6.2 SUMMARIES OF CONDUCT OF STUDY

Enrolment, screening failures, ocrelizumab administration, and discontinuations from the study will be summarized using descriptive statistics (frequency tables for categorical endpoints and mean, median, range, standard, deviation [SD] and 25th-75th quartiles for the continuous endpoints). Patient disposition and the incidence of treatment discontinuation for different reasons will be tabulated. Major protocol violations, including violations of inclusion/exclusion criteria, will also be summarized.

6.3 SUMMARIES OF DEMOGRAPHIC AND BASELINE CHARACTERISTICS

Patients' demographics (age, gender, and self-reported race), medical history and neurological examination will be summarized. The following will also be summarized: MS disease history (duration since first MS symptoms, duration of MS since diagnosis, relapses in the past year), baseline measures of MRI, EDSS and other important variables.

6.4 EFFECTIVENESS ANALYSES

6.4.1 Effectiveness Endpoints

Effectiveness of ocrelizumab will be evaluated by means of a set of endpoints addressing different facets of MS. There is no primary endpoint defined in the main study. These effectiveness endpoints include time to onset of confirmed CDP sustained for at least 24 and 48 weeks, change from baseline in EDSS score over time, relapse rates, MRI-based measures of disease activity and progression or degeneration, measures of cognition and PROs.

For a full list of effectiveness endpoints refer to Section 2.

After the Week 192 visit of the last enrolled patient, approximately 24 weeks and 48 weeks may be needed to allow the confirmation of the last event of the 24-week and 48 week-CDP (CDP/CDI confirmation visit). The main study analysis will be performed after the last CDP and CDI confirmation visit. With respect to CDP confirmation visits, only EDSS data at all the visits occurring in the treatment period of the study and LTE study (for patients who roll over to study MN39158) will be used. Appropriate statistical methods to account for missing confirmation visits will be defined in the SAP.

The evaluation of the clinical effectiveness of ocrelizumab will be based upon the events and assessments in-between baseline and week 192.

For patients who do not have an event by week 192, the time-to-event endpoints will be censored at the time of last visit in the study. A descriptive analysis based on the Kaplan-Meier method will be performed for the time to CDP and other time-to-event endpoints, such as the time to first relapse or the time to first event of disease activity. Cox proportional hazards regression will be used to identify predictors for CDP and other time-to-event endpoints. Variables to be included in the regression model will be region, gender, baseline EDSS, and some other variables, as appropriate. Further details will be specified in the SAP.

The change from baseline in EDSS, as well as other continuous variables, will be primarily analyzed using descriptive statistics, the mean, corresponding 95% CI, standard deviation and other statistics will be presented. Furthermore, the change of EDSS from baseline to each visit will be analyzed by linear mixed models for repeated measures (MMRM) adjusting for covariates such as the respective baseline score, geographical region, and baseline EDSS.

Ocrelizumab—F. Hoffmann-La Roche Ltd 87/Protocol MA30143, Version 10.0 MRI activity will be evaluated from week 8 (baseline for MRI-based endpoints) to week 192.

For binary endpoints, e.g., NEP, NEDA and NEPAD, the proportion of patients meeting the endpoint at Week 96, 144 and 192 will be calculated and the corresponding twosided Clopper-Pearson 95% CI will be presented. Logistic regression models will be used to identify prognostic factors.

The annualized relapse rates will be analyzed using a Poisson regression model, adjusting for region and baseline EDSS. The total number of T1 Gd-enhanced lesions will be calculated as the sum of the individual number of T1 Gd-enhanced lesions at Weeks 24, 48, 96, 144 and 192. A Poisson model will be used to estimate the rate of lesion occurrence. A quasi Poisson or negative binomial regression may be applied as a sensitivity analysis.

An analysis of individual components of the composite endpoint will also be performed.

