- Antihistamine via oral, intramuscular or IV route to be completed approximately 30-60 minutes and not less than 25 minutes prior to each infusion of ocrelizumab (the antihistamine should be the first premedication to be administered).
- The addition of an antipyretic (e.g., acetaminophen/ paracetamol) may also be considered.

Statistical Methods

Primary Analysis

The main study is an open-label single-arm study. No formal confirmatory hypothesis test will be conducted.

The intent-to-treat (ITT) population will include all enrolled patients who received any dose of ocrelizumab and will be used for the primary analyses of effectiveness and safety. The perprotocol (PP) population will include all ITT patients without major protocol deviations deemed to potentially affect the effectiveness endpoints. The PP population will be used for supportive effectiveness analyses. Safety population is defined as all enrolled patients who received any dose or part of a dose of ocrelizumab in the study. After the Week 192 visit of the last enrolled patient, approximately 24 weeks and 48 weeks may be needed to allow the confirmation of the last event of the 24 week and 48 week-CDP (CDP/CDI confirmation visit). The analysis will be performed after the last CDP and CDI confirmation visit. With respect to CDP confirmation visits, only EDSS data at all the visits occurring in the treatment period of the study and LTE study (for patients who roll over to study MN39158) will be used. Appropriate statistical methods to account for missing confirmation visits will be defined in the statistical analysis plan (SAP).

The evaluation of the clinical effectiveness of ocrelizumab will be based upon the events and assessments in-between the baseline and week 192. The MRI activity will be evaluated from week 8 (baseline for MRI-based endpoints) to week 192. For the patients who do not have an event, time-to-event endpoints will be censored at the time of last visit in the study. A descriptive analysis based on the Kaplan-Meier method will be performed for the time to CDP and other time-to-event endpoints, such as the time to first relapse or to first event of disease activity. Change of EDSS from baseline at week 192 will be analyzed based on mixed models for repeated measures. Details will be specified in the SAP.

Determination of Sample Size

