Figure 2 **Overview of End of Treatment Period** *provides an overview of the end-of-treatment period.* (*Please see Section* 3.1.4).

A structured telephone interview will be conducted by site personnel every 8 weeks between the study visits (starting after the site visit at 8 weeks) during the treatment period to identify and collect information on any changes in the patient's health status that warrant an unscheduled visit (including new or worsening neurological symptoms) and possible events or infections.

LTE = *Long-term extension; MS* = *Multiple sclerosis*

3.1.4 Safety Follow-up Period

Patients who discontinue treatment early for any reason and patients who complete the 192 weeks Treatment Period and do not continue in a separate LTE study will be followed up for 48 weeks after the last infusion of study drug. When patients begin an alternative treatment for MS (see section 4.4.1 "Prohibited Therapy"), they will be discontinued from the study.

Patients who discontinue study treatment and switch to commercially marketed ocrelizumab, either after completion of the 192 weeks Treatment Period or after early discontinuation of the 192 weeks Treatment Period, will not enter the *Safety* Follow-up Period.

A schedule of assessments for the *Safety* Follow-up Period is presented in Appendix 2.

During the *Safety* Follow-up Period, patients will be formally assessed at clinical visits every 24 weeks.

Ocrelizumab—F. Hoffmann-La Roche Ltd 37/Protocol MA30143, Version 10.0 Related SAEs must be collected and reported regardless of the time elapsed from the last study drug administration, even if the study has been closed.

Unrelated SAEs must be collected and reported during the study through the end of the Safety Follow-Up Period, which is 48 weeks after the last infusion. Non-serious adverse events have to be reported until the end of Safety Follow-up Period.

For patients withdrawing from treatment early, every effort should be made to complete the *Safety* Follow-up Period and all related assessments.

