4.5.6 Assessment of Disability

Disability in MS will be measured by the EDSS and MSFC. See Appendix 1 (Schedule of Assessments) for the timing of these assessments.

The EDSS is based on a standard neurological examination, incorporating seven functional systems (pyramidal, cerebellar, brainstem, sensory, bowel and bladder, visual, and cerebral rated and scored as FSS. Each FSS is an ordinal clinical rating scale ranging from 0 to 5 or 6. These ratings are then used in conjunction with observations and information concerning ambulation and use of assistive devices to determine the EDSS score (*i.e., ambulation score 0 to 12*). When determining the EDSS step, the Visual and the Bowel and Bladder FSS will be converted to a lower score as per the Neurostatus instructions. The original unconverted score should be recorded in the respective eCRF page. The EDSS is a disability scale that ranges in 0.5-point steps from 0 (normal) to 10 (death) (see Appendix 3).

Disability progression has been defined as an increase of ≥ 1.0 point from the baseline EDSS score that is not attributable to another etiology (e.g., fever, concurrent illness, or concomitant medication) when the baseline score is 5.5 or less, and ≥ 0.5 when the baseline score is above 5.5. For patients with an EDSS of 0, progression is defined as a change >=1.5 points Disability progression is considered confirmed when the increase in the EDSS is confirmed at a regularly scheduled visit at least 24 weeks after the initial documentation of neurological worsening.

Ocrelizumab—F. Hoffmann-La Roche Ltd 54/Protocol MA30143, Version 10.0

CDI is defined as an improvement of 1 point on the EDSS score confirmed at a regular scheduled visit at least 24 weeks after the initial documentation of neurological worsening (measured only patients with a baseline EDSS of \geq 2.0).

Stable disability is defined as a difference in EDSS score of no greater than ± 0.5 at the end of each year compared with baseline scores, worsened disability as an increase in EDSS score of > 0.5 at the end of each year compared with baseline, and improved disability as a reduction in EDSS score of > 0.5 at the end of each year compared with baseline.

MSFC is a score combining a measure of lower limb function (T25FWT), upper limb function (9HPT) and cognitive function (PASAT) used to detect disability progression in MS trials.

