6.1 DETERMINATION OF SAMPLE SIZE

The main study is a single-arm effectiveness and safety study. There is no formal statistical hypothesis and all analyses will be descriptive. The results for the key endpoints will be presented in a descriptive analysis including the corresponding 95% the confidence intervals.

Sample size considerations for the main study are based on pooled data from two ocrelizumab phase III trials in RRMS (OPERA I and II). Based on extrapolations from these studies, we can conservatively expect 15% of patients (or less) to have a CDP event and approximately the same number of patients to be prematurely withdrawn and censored before week 192.

In this case, for 1,100 patients, the precision (half-width of the 95% confidence interval) of the estimated CDP rate by study end is expected to be approximately 1.8%, i.e., the 95% confidence interval of (13.2%, 16.8%).

In OPERA the EDSS improvement at 2 years had a standard deviation of 0.74, based on 240 patients from the ocrelizumab group, who were previously treatment-naïve with disease duration \leq 3 years and EDSS \leq 3.5. The standard deviation was rather stable over time and is assumed to remain stable after four years of treatment. A sample size of 1,100 patients is expected to provide a precision for the estimate of the EDSS change from baseline of about 0.037, assuming a standard deviation of 0.75. Assuming no EDSS change from baseline, the 95% confidence interval is expected to be (-0.074, 0.074).

The main study was initially planned to enroll at least 600 patients. Approximately 550 additional patients were to be enrolled in the shorter infusion sub-study. They would also be enrolled in the main study (see Appendix 10 for more details). Therefore, the main study would enroll a total of at least 1,100 patients. A total of 1,225 patients (678 in the main study and 547 in the shorter infusion substudy) were enrolled in the study.

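### Event-free patients are censored for CDP at the last study visit, which for early discontinuers can be a safety follow-up visit that cannot yield a countable CDP, so the Kaplan-Meier rate is slightly too low

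*Protocol*

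**What the plan says.** Protocol Section 6.4.1 plans a descriptive Kaplan-Meier analysis of time to CDP over baseline to Week 192. For confirmation visits it uses "only EDSS data at all the visits occurring in the treatment period of the study and LTE study" (the LTE, for patients who roll over). Under Section 4.5.6 a worsening must be "confirmed at a regularly scheduled visit at least 24 weeks after the initial documentation of neurological worsening".

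Section 6.4.1 then says that for patients with no event by Week 192, "the time-to-event endpoints will be censored at the time of last visit in the study". The Primary Analysis part of the synopsis repeats this: "For the patients who do not have an event, time-to-event endpoints will be censored at the time of last visit in the study".

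Safety follow-up belongs to the study: Section 3.1 lists it as a study period, and Section 3.2 uses it to define the end of the study. Section 3.1.4 says that early discontinuers, and completers who "do not continue in a separate LTE study will be followed up for 48 weeks after the last infusion of study drug". Appendix 2 schedules EDSS for early discontinuers 24 and 48 weeks after the last infusion. Footnote c on that EDSS row repeats the sentence about the time needed to confirm the last CDP events, without saying whether follow-up EDSS may serve for this.

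Two groups do not contribute follow-up time. Of patients who start another MS therapy, Section 3.1.4 says "they will be discontinued from the study". Those who switch to commercial ocrelizumab do not enter follow-up.

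**The concern.** The visits that can supply a CDP and the visits that define time at risk are not the same set. A worsening first seen in safety follow-up would need a later treatment-period or LTE EDSS to confirm it, and a patient in follow-up has none. If the follow-up visit sets the censoring date, the patient stays in the denominator over an interval in which the numerator cannot increase.

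Section 3.3 calls time to CDP one of the key outcome measures. The main study has a single arm, so there is no comparator in which the bias could cancel. Unlike sampling error, it always favours the drug and does not shrink as the sample grows.

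**Working it through.** **The plan's own figure.** Section 6.1 expects a 15% CDP rate in 1,100 patients and says "the precision (half-width of the 95% confidence interval) of the estimated CDP rate by study end is expected to be approximately 1.8" per cent. The binomial formula gives 1.96 × √(0.15 × 0.85 / 1100) = 2.11 points. The stated value matches a 90% interval: 1.645 × √(0.15 × 0.85 / 1100) = 1.77. That mismatch is a separate matter; 2.1 points is used below only as a yardstick.

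**Inputs from the documents.**
- CDP rate by Week 192: 15% (Section 6.1).
- Early leavers: w = 15%. Section 6.1 expects "approximately the same number of patients to be prematurely withdrawn and censored before week 192".
- EDSS every 24 weeks, Weeks 24 to 192, so eight visits k = 1 to 8 (Appendix 1).

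**Assumptions.**
- Constant hazard and non-informative withdrawal.
- Each leaver's last treatment-period EDSS is spread evenly over Weeks 24 to 168 (seven visits).
- All completers enter the LTE.
- A share a of leavers attends follow-up, and the last study visit falls 24 weeks after the last treatment-period EDSS. This would be so if that EDSS were done 24 weeks after the last infusion and the 48-week follow-up visit were attended.

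**Formulas.** Hazard per visit: h = 1 − 0.85^(1/8) = 0.0201. To isolate the effect of follow-up time, a worsening at the last treatment-period EDSS is treated as countable. As fractions of the starting cohort, with the common survival factor cancelling:
- able to have a countable event at visit k: P_k = (1 − w) + w(8 − k)/7
- at risk but unable to: I_k = a × w/7 for k ≥ 2, and 0 for k = 1
- hazard as estimated: h × r_k, with r_k = P_k / (P_k + I_k)
- Kaplan-Meier rate at Week 192: 1 − ∏(1 − h × r_k)

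With a = 1, r_1 = 1, r_2 = 0.97857/1.00000 = 0.9786, and so on down to r_8 = 0.85000/0.87143 = 0.9754.

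| Leavers attending follow-up | KM rate (true 15.00%) | Shortfall, points |
|---|---|---|
| 100% | 14.72% | 0.28 |
| 50% | 14.86% | 0.14 |
| 25% | 14.93% | 0.07 |

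With I_k = 0 the formula returns 15.00%, so censoring at the last treatment-period EDSS removes the shortfall.

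**Sensitivity.**
- If worsenings at the last treatment-period EDSS are lost for want of confirmation, the follow-up effect is unchanged: 14.72% against 14.44% for 24-week CDP and 14.48% against 14.19% for 48-week CDP, 0.28 points in each case after rounding.
- With 10% or 20% leaving early and all attending: 0.18 or 0.38 points.
- With a 48-week gap and all attending: 14.72% against 14.20%, or 0.52 points. If instead the last treatment-period EDSS is on the day of the last infusion and last infusions are spread over Weeks 0 to 144, the figure is 0.56.
- If the early-discontinuation EDSS (Appendix 1) is done later than assumed, the gap and the effect shrink.

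**Completers.** The last planned infusion is at Week 168, so a completer's follow-up visit falls at 168 + 48 = Week 216. That is after Week 192 and does not affect the Week 192 estimate.

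**The case against.** The strongest reply is that Section 6.4.1 ends this paragraph by leaving further details to the SAP, and Section 6 leaves all statistical detail to it. The SAP supplied covers only the shorter infusion substudy and plans no efficacy analysis, so a main-study SAP might define the censoring date properly. It might, and a reader should not infer that the final analysis is wrong. But the protocol fixes the date in two places, and a general deferral does not undo that.

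The second reply is that few leavers will attend follow-up. This stands in part. Section 6.1 describes its 15% as withdrawn, not as follow-up attenders, and Section 3.1.4 keeps commercial switchers and patients on another MS therapy out. So 0.28 is close to a ceiling for a 24-week gap. The group is not empty, though: Section 4.7.1 sends patients who stop to plan a pregnancy into follow-up, and Section 3.1.4 asks for every effort to complete it.

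A reader might also infer a larger shortfall by adding worsenings first seen at the last treatment-period visit, which cannot be confirmed without LTE entry. In the same model the totals would be 0.56 points (24-week CDP) and 0.81 points (48-week CDP). The documents do not support charging that to the plan: Section 6.4.1 expressly leaves missing confirmation visits to the main-study SAP, and the choice of method is open to debate.

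**Conclusion.** The censoring rule as written does not fit the confirmation rule, and the mismatch lowers the Week 192 Kaplan-Meier CDP rate. The size is about 0.07 to 0.28 points for 25% to 100% attendance with a 24-week gap, and about 0.5 points at most with a 48-week gap. That compares with a half-width of about 2.1 points; 0.28/2.11 is 13% of it.

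The direction follows from the two rules alone, provided follow-up EDSS cannot confirm CDP. The size rests on the protocol's 15% and 15%, on non-informative withdrawal, and on an attendance share and gap that the documents do not give. Severity is minor: the study is descriptive, has no primary endpoint, and the effect is small against its precision. The point concerns time to 24-week and 48-week CDP only.

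**What to change.** In Section 6.4.1 and the synopsis, for time to 24-week and to 48-week CDP, change the censoring date for event-free patients from the last study visit to the last treatment-period or LTE EDSS assessment, capped at Week 192. Carry the same rule into the main-study SAP.

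State whether safety follow-up EDSS may confirm CDP, and bring footnote c of Appendix 2 into line with Section 6.4.1.

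The cost is wording only, with no new data or visits. The one downside for the sponsor is that the reported CDP rate becomes very slightly less favourable.

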6.8 HANDLING OF MISSING DATA

Patients not completing the study for reasons different from lack of effectiveness or death will be defined as not reaching the NEDA endpoint ("NEDA=no"). The same rule will be used for NEP and NEPAD. More details about the missing data handling will be specified in statistical analysis plan.

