Patients who provide consent to participate in this substudy and fulfill eligibility criteria will provide additional blood samples at baseline, 24 weeks, 48 weeks, end of treatment period (192 weeks or earlier in case of study withdrawal), every 24 weeks *for 48 weeks* after last *infusion of* ocrelizumab and in case of unscheduled visit due to relapse, as indicated in the schedule of assessments.

Blood samples can be collected 2 weeks (± 4 days) prior to ocrelizumab infusion, in addition to laboratory samples required in the main study.

12 tubes of 8mL each will be drawn at each time points. Samples will be prepared and frozen at investigational centers and sent to Nantes CHU for in vitro analyses.

Number of Patients

The number of patients enrolled in this MA30143 substudy is \sim 50 patients. Patients enrolled in study MA30143 and recruited in specific centers in France will be offered to participate in this substudy.

Participating centers are restricted to French investigator centers with PBMC (peripheral blood mononuclear cell) technical and storage capacity.

The number of patients that will withdraw from the study is estimated to be 10 (20% withdrawal rate over 192 weeks). As a consequence, approximately 10 patients would enter the follow-up period for B cell repletion. Patients will provide blood samples every 24 weeks *for 48 weeks* after last ocrelizumab infusion.

Ocrelizumab—F. Hoffmann-La Roche Ltd

137/Protocol MA30143, Version 10.0

Target Population

Inclusion Criteria

Patients must meet the following criteria to be eligible for substudy entry:

- Enrolled in the Phase IIIb study MA30143
- Signed Informed Consent Form for the MA30143-T and B cell Substudy France
- Able to comply with the substudy protocol, in the investigator's judgment.

Exclusion Criteria

There is no exclusion criteria beyond those listed in the main protocol of the MA30143 study.

End and length of the substudy

The end of the substudy is defined as the last patient visit. *in the Safety Follow-up period or last patient Week 192 visit, whichever occurs later.*

The maximum length of the study, from screening of the first patient to the end of the substudy, is expected to be approximately 316 weeks (6.5 years). This includes an enrolment period of approximately 76 weeks.

Investigational Medicinal Products

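### The exploratory logistic models for prognostic factors count event-free withdrawals as failures, mixing predictors of leaving with predictors of progression; the uncovered part is NEP (walk and peg tests) and NEPAD

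*Protocol*

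**What the plan says.** Protocol Section 6.4.1 introduces the binary endpoints: "For binary endpoints, e.g., NEP, NEDA and NEPAD, the proportion of patients meeting the endpoint at Week 96, 144 and 192 will be calculated", with Clopper-Pearson intervals. It then adds "Logistic regression models will be used to identify prognostic factors". It names no covariates for these models and gives no alternative outcome coding.

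Section 6.8 fixes the coding: "Patients not completing the study for reasons different from lack of effectiveness or death will be defined as not reaching the NEDA endpoint". It extends this to the other two endpoints: "The same rule will be used for NEP and NEPAD". It does not say how withdrawals for lack of effectiveness or death are coded, and it leaves further missing-data detail to the SAP. Section 6 keeps early withdrawals in the ITT population.

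For time-to-event endpoints Section 6.4.1 takes a different route. Patients without an event are censored at their last visit, and "Cox proportional hazards regression will be used to identify predictors for CDP and other time-to-event endpoints". Time to first protocol-defined disease activity is one of these endpoints, and Section 2 builds it from the same four components as NEDA. Section 6.4.1 also promises an analysis of the individual components of the composite, without a method.

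Section 6.1 supplies the only planning rates. Its CDP assumption reads: "we can conservatively expect 15% of patients (or less) to have a CDP event". For losses from the study, its working assumption is "approximately the same number of patients to be prematurely withdrawn and censored before week 192".

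**The concern.** As a rule for a reported proportion, counting a withdrawal as a failure is an ordinary conservative choice. It is not conservative for a regression coefficient. A patient who moves away with no relapse, no progression and no new lesion enters the logistic model with the same outcome as a patient who progressed. The model then describes who progresses or leaves, while the Cox models in the same section censor that patient.

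Two errors follow. A baseline factor related only to leaving can look prognostic, and a genuine prognostic factor is pulled towards no effect. The protocol itself gives routes by which leaving could depend on baseline factors. Patients planning pregnancy stop treatment and do not restart (Sections 4.7.1 and 5.4.3.1). Patients may move to commercially marketed ocrelizumab (Section 3.1), whose approval differs by country (Section 5.1). The documents give no size for either route and do not say outright that every such exit counts as not completing the study.

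**Working it through.** **Inputs from the documents.** CDP 15% and withdrawal without CDP about 15% by Week 192, with n = 1,100 planned (Section 6.1); 1,225 enrolled; coding rule from Section 6.8. The plan states no failure rate for NEP, NEDA or NEPAD and no dropout share, so there is no planned figure to reproduce.

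**Assumptions made here.** True progression of 20% or 30% for NEP when walk and peg-test failures are added; 50% true failure for NEDA or NEPAD; a binary factor held by half the patients; withdrawal odds ratios of 1.2, 1.5 and 2.

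**Step 1. Share of failures that are dropouts** = w/(w + p), where w is withdrawal and p is observed failure.

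- p = 15% (CDP only): 15/30 = 50%, or 165 of 330 patients
- p = 20%: 15/35 = 43%
- p = 30%: 15/45 = 33%
- p = 50% (NEDA or NEPAD): 15/65 = 23%

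The 50% moves both ways. If 10% to 30% of withdrawals are for lack of effectiveness or death and fall outside the rule, it becomes 13.5/28.5 = 47% down to 10.5/25.5 = 41%. With the "20% withdrawal rate over 192 weeks" assumed for the French substudy in Appendix 8, it becomes 20/35 = 57%.

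**Step 2. Spurious association.** The factor changes the odds of withdrawal by the stated ratio and has no effect on progression. Withdrawal in its two levels, w0 and w1, averages 15%. Progression among those who stay is q = p/0.85. The failure probability is f = w + (1 − w)q. The odds ratio comes from f0 and f1, with SE = √[1/(550·f0(1 − f0)) + 1/(550·f1(1 − f1))].

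Worked case, withdrawal odds ratio 2 and p = 15%: q = 0.1765; f0 = 0.1069 + 0.8931 × 0.1765 = 0.264; f1 = 0.1931 + 0.8069 × 0.1765 = 0.336; odds ratio 1.40; log 0.339; SE 0.132; z = 2.57. The chance of p<0.05 is Φ(2.57 − 1.96) ≈ 73%.

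| Withdrawal OR | w0, w1 | Failure, two levels | Spurious OR | p<0.05 |
|---|---|---|---|---|
| 1.2 | 13.8%, 16.2% | 29.0%, 31.0% | 1.10 | 11% |
| 1.5 | 12.4%, 17.6% | 27.9%, 32.1% | 1.22 | 33% |
| 2 | 10.7%, 19.3% | 26.4%, 33.6% | 1.40 | 73% |

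At a withdrawal odds ratio of 2, raising p to 20%, 30% or 50% gives spurious odds ratios of 1.34, 1.25 or 1.17 and p<0.05 in 63%, 46% or 23%. With 1,225 patients and p = 15%, 2,000 simulated trials gave an odds ratio of 1.41 and p<0.05 in 77%.

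**Step 3. Dilution.** Take a true progression odds ratio of 2 with 15% withdrawal in both levels. At p = 15%, progression among those who stay is 12.7% and 22.6%. Failure is 0.15 + 0.85 × 0.127 = 25.8% and 0.15 + 0.85 × 0.226 = 34.2%, an odds ratio of 1.49. At p = 20% or 30% it is 1.58 or 1.72.

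**Step 4. After removing the coding.** In the same simulation, leaving withdrawals out brought p<0.05 to 5.3%, provided withdrawal is independent of progression given the factor. If only event-free withdrawals are dropped and half of the dropouts' events occur before they leave, a small bias remains. The residual odds ratio is [1 + 0.1931/(2 × 0.8069)] / [1 + 0.1069/(2 × 0.8931)] = 1.120/1.060 = 1.06.

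**The case against.** The strongest reply is that much of this is already covered. The Cox model for time to first disease activity is a censored analysis of NEDA's own components, and the Cox model for CDP covers that part of NEP. This stands. What it leaves uncovered is the walk and peg-test components of NEP, and NEPAD as a composite. The component analysis may help, but it has no stated method and does not alter the logistic outcomes.

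Second, everything here is exploratory. Section 6 calls the tests exploratory and applies no multiplicity correction. Predictors of progression are an exploratory endpoint in Section 2, and no decision depends on these models. This limits the weight of the point. A reader might infer that the study fails a stated aim of finding prognostic factors. The documents do not support that: the primary objective is effectiveness, and the Cox models still address prognosis.

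Third, the effect sizes are assumed. No document gives a factor that doubles the odds of withdrawal, and at an odds ratio of 1.2 the false-positive rate is only 11%. A reader might infer that region, age or sex will be reported as prognostic. The protocol shows only that such links are possible.

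Fourth, completing without an event is a coherent composite. That is fair if the model is labelled that way, but Section 6.4.1 presents it as identifying prognostic factors.

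Finally, the main-study SAP is not among the documents; the one supplied covers the shorter infusion substudy. It may add restricted or sensitivity models.

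**Conclusion.** The concern holds as a limited point about exploratory models: a factor tied only to leaving can appear prognostic, and real effects are diluted.

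A reader might infer from the plan's rates that half of all NEDA, NEP and NEPAD failures are dropouts. The documents do not support this. The 50% applies to NEP at Week 192, with nobody failing on the walk or peg test alone and every withdrawal falling under the 6.8 rule. The share is lower for NEDA and NEPAD, which add relapse and MRI failures. Nor is 50% a strict ceiling, since higher withdrawal would raise it.

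The false-positive rates rest on the assumed prevalence and withdrawal odds ratios. The direction of the error does not depend on their exact size, but it arises only for factors related to withdrawal.

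**What to change.** - Keep the Section 6.8 coding for the reported proportions.
- For prognostic factors, extend the Cox approach of Section 6.4.1 to time to first NEP component event and time to first NEPAD component event. Censor event-free withdrawals at the last visit at which all components were assessed.
- For NEDA, rely on the Cox model already planned for time to first disease activity.
- If the logistic models are kept, label them as models of completing without an event. Add a sensitivity model that leaves out patients who fail only through the 6.8 rule, and note that a small residual bias can remain.
- State how withdrawals for lack of effectiveness or death are coded.

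The cost is wording in the main-study SAP and a few extra models; no new data are needed. The downside is that censoring assumes withdrawal is non-informative given the covariates. If the main-study SAP already does this, a cross-reference from Section 6.4.1 is enough.
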